### **Diagnostic Assessments**

- 19. More than one LDH value  $> 2 \times$  ULN within the 6 months prior to Day 1.
- 20. Platelet count <  $30,000/\text{mm}^3$  ( $30 \times 10^9/\text{L}$ ) at Screening.
- 21. Absolute neutrophil count  $< 500/\mu L (0.5 \times 10^9/L)$  at Screening.
- 22. Positive human immunodeficiency virus (HIV) antibody test.

### **Other Exclusions**

23. Females who plan to become pregnant, are currently pregnant or breastfeeding, or are sexually active and unwilling to use effective birth control for the duration of the study.

### 5.3. Lifestyle Considerations

No restrictions are required.

### 5.4. Screen Failures

Screen failures are defined as participants who consent to participate in the clinical study but are not subsequently entered in the study. A minimal set of screen failure information is required to

ensure transparent reporting of screen failure participants to meet the Consolidated Standards of Reporting Trials (CONSORT) publishing requirements (Schulz, 2010) and to respond to queries from regulatory authorities. Minimal information includes demography, screen failure details (eg, failed eligibility criteria), and any AEs or SAEs occurring during the Screening Period.

Individuals who do not meet the criteria for participation in this study (screen failure) due to a reason that is expected to resolve or has resolved may be rescreened based on discussion and agreement between the Investigator and Medical Monitor.

### 6. STUDY TREATMENTS

Study drug is defined as any investigational drug(s), marketed product(s), placebo, or medical device(s) intended to be administered to a study participant according to the study protocol.

### 6.1. Study Drug(s) Administered

Ravulizumab is a humanized, anti-C5a mAb. Ravulizumab was derived through minimal targeted engineering of eculizumab by introducing 4 unique amino acid substitutions to its heavy chain. Ravulizumab and eculizumab share over 99% primary sequence identity and have very similar pharmacology.

Ravulizumab drug product is supplied for clinical studies as a 10-mg/mL solution in a 30-mL single-use vial and is designed for infusion by diluting into commercially available saline (0.9% sodium chloride injection; country-specific pharmacopeia) for administration via IV infusion.

Each vial of ravulizumab drug product includes a nominal overfill to ensure that 30 mL (300 mg of the ravulizumab antibody) of solution can be withdrawn for IV administration.

ARM Name	Ravulizumab				
Drug Name	Ravulizumab				
Туре	Biologic				
Dose Formulation Concentrated sterile, preservative-free aqueous solution					
Unit Dose Strength(s)300 mg (10 mg/mL concentrated solution)					
Dosage Level(s)	Doses based on participant weight				
Route of Administration	IV infusion				
Use	Experimental				
IMP and NIMP	IMP				
Sourcing	Provided centrally by Alexion or contracted manufacturing organization.				
Packaging and Labeling	Study drug will be provided in glass vials and stoppered with a butyl rubber				
	stopper with an aluminum overseal and a flip-off cap. Study drug will be supplied				
	in kits and labeled as required per country requirement.				

Abbreviations: IMP = investigational medicinal product; IV = intravenous; NIMP = non-investigational medicinal product

#### 6.1.1. Ravulizumab Dosing

The approved body weight-based ravulizumab dosing is shown in Table 4.

Dose Type	Body Weight (kg) a	Dose (mg)	Ravulizuma b Volume (mL)	Saline Volume (mL)	Total Volume (mL)	Minimum Infusion Duration minutes (hours)	Maximum Infusion Rate (mL/hour)
Loading	$\geq$ 40 to < 60	2400	240	240	480	114 (1.9)	253
	$\geq$ 60 to < 100	2700	270	270	540	102 (1.7)	318
	≥100	3000	300	300	600	108 (1.8)	333
Maintenance	$\geq$ 40 to $<$ 60	3000	300	300	600	140 (2.4)	250
	$\ge 60 \text{ to} < 100$	3300	330	330	660	120 (2.0)	330
	≥100	3600	360	360	720	132 (2.2)	328

 Table 4:
 Dosing Reference Chart for Ravulizumab Dose Preparation

Note: Please refer to the Pharmacy Manual for additional dose preparation instructions.

a Dose regimen will be based on the last recorded study visit body weight.

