# 6.2. Preparation/Handling/Storage/Accountability

Upon arrival of the study drug at the study site, study drug kits should be removed from the shipping container and stored in their original cartons under refrigerated conditions at 2°C to 8°C (35°F to 47°F) and protected from light. Ravulizumab should not be frozen.

Study drug must be stored in a secure, limited-access storage area with temperature monitored daily.

Infusions of study drug should be prepared using aseptic technique. Ravulizumab will be further diluted in a 1:1 ratio with compatible diluent. Ravulizumab will be filtered with a 0.2 micron filter during infusion. Study drug will be prepared and administered by a trained member of the site study team.

- 1. The investigator or designee must confirm appropriate temperature conditions have been maintained during transit for all study drug received and any discrepancies are reported and resolved before use of the study drug.
- 2. Only participants enrolled in the study may receive study drug and only authorized site staff may supply or administer study drug. All study drug must be stored in a secure, environmentally controlled, and monitored (manual or automated) area in accordance with the labeled storage conditions with access limited to the investigator and authorized site staff.
- 3. The investigator, institution, or the head of the medical institution (where applicable) is responsible for study drug accountability, reconciliation, and record maintenance (ie, receipt, reconciliation, and final disposition records).
- 4. For detailed instruction on study drug preparation, handling, storage, and accountability, refer to the Pharmacy Manual. Further guidance and information for the final disposition of unused study drug are provided in the Pharmacy Manual.

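### Protocol Table 4, maintenance row for 40 to <60 kg: 140 minutes is not 2.4 hours, and an infusion timed to 140 minutes exceeds the row's own 250 mL/hour maximum (minor)

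*Protocol*

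**What the plan says.** Table 4 in Protocol Section 6.1.1 sets out dose, volumes and infusion limits for three weight bands, separately for loading and maintenance doses. The two limit columns are headed "Minimum Infusion Duration minutes (hours" (the bracket closes after hours) and "Maximum Infusion Rate (mL/hour" (per hour of infusion).

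The maintenance row for 40 to <60 kg reads "3000 300 300 600 140 (2.4) 250". In order, these are the dose in mg, the ravulizumab, saline and total volumes in mL, the minimum duration in minutes with hours in brackets, and the maximum rate. The part at issue is the last three entries, "600 140 (2.4) 250".

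The ravulizumab administration rows of the q8w and q6w schedules (Protocol Section 1.3, Tables 2 and 3) send staff to Section 6.1.1 for dosing. Neither the protocol nor the SAP gives an infusion duration or rate anywhere else. A note under Table 4 refers to the Pharmacy Manual for further preparation instructions; that manual is not among the documents available here.

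**The concern.** The minutes and the bracketed hours are meant to be the same time in two units, and in this row they are not. In addition, the minimum duration and the maximum rate should describe the same boundary for a fixed volume. Here, staff who time the infusion to the printed minimum minutes run it faster than the printed maximum rate.

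What is at stake is the clarity of an administration chart for one weight band. The row covers six scheduled q8w maintenance infusions per participant in that band (Days 15, 71, 127, 183, 239 and 295 in Table 2), plus any supplemental doses (Section 6.6.1) or q6w doses (Section 6.6.2). The documents do not say how many participants fall in the band, so no total can be given.

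**Working it through.** **Inputs.** Volumes, minutes, hours and rates are those printed in Table 4. Two statements elsewhere confirm the volume: the product strength in Section 6.1, "300 mg (10 mg/mL concentrated solution", and the dilution rule in Section 6.2, "Ravulizumab will be further diluted in a 1:1 ratio with compatible diluent".

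**Step 1: volume.** 3000 mg ÷ 10 mg/mL = 300 mL of ravulizumab. Adding an equal volume of diluent gives 300 + 300 = 600 mL, as printed. The volume is not in doubt.

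**Step 2: minutes against hours.** 140 ÷ 60 = 2.333 h, which rounds to 2.3, not 2.4. In the other direction, 2.4 × 60 = 144 min. Times that round to 2.4 h to the nearest tenth run from 2.35 × 60 = 141 min to 2.45 × 60 = 147 min, so rounding to nearest does not produce 140.

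**Step 3: minutes against rate.** 600 ÷ (140/60) = 257.14 mL/h. This exceeds the printed 250 by 7.14 mL/h, and 7.14/250 = 2.86%. In the other direction, 600 ÷ 250 × 60 = 144.0 min, a gap of 4.0 min. If 250 is itself a rounded figure (249.5 to 250.5), the time is 143.7 to 144.3 min, which still excludes 140.

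**Step 4: the same tests on all six rows.** For example, the first two loading rows read "480 114 (1.9) 253" and "540 102 (1.7) 318".

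| Row | Volume (mL) | Printed min (h) | Min ÷ 60 (h) | Volume ÷ printed time (mL/h) | Printed rate (mL/h) | Volume ÷ printed rate (min) | Difference from printed min |
|---|---|---|---|---|---|---|---|
| Loading, 40 to <60 kg | 480 | 114 (1.9) | 1.90 | 252.63 | 253 | 113.83 | -0.17 |
| Loading, 60 to <100 kg | 540 | 102 (1.7) | 1.70 | 317.65 | 318 | 101.89 | -0.11 |
| Loading, ≥100 kg | 600 | 108 (1.8) | 1.80 | 333.33 | 333 | 108.11 | +0.11 |
| **Maintenance, 40 to <60 kg** | **600** | **140 (2.4)** | **2.33** | **257.14** | **250** | **144.00** | **+4.00** |
| Maintenance, 60 to <100 kg | 660 | 120 (2.0) | 2.00 | 330.00 | 330 | 120.00 | 0.00 |
| Maintenance, ≥100 kg | 720 | 132 (2.2) | 2.20 | 327.27 | 328 | 131.71 | -0.29 |

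In the other five rows the minutes are exactly 60 times the hours. The largest rate difference among them is 0.73 mL/h (0.22%) and the largest time difference is 0.29 min, both in the ≥100 kg maintenance row, where 327.27 is printed as 328. The 40 to <60 kg maintenance row is the only one that fails by more than rounding.

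**The case against.** Four points can be made on the other side.

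- **Both limits can be met together.** They are one-sided bounds, and any infusion at or below 250 mL/hour satisfies the minutes, the hours and the rate. This stands, and it limits the consequence. It does not make the cell consistent: the two limits should coincide for a fixed volume, and timing to the printed minutes breaks the printed rate.
- **Rounding may explain the figures.** Rounding 2.33 h up to 2.4 and then taking 600 ÷ 2.4 = 250 would produce the row. The loading row for ≥100 kg also runs slightly over its maximum if timed to its minimum (333.33 against 333), so a small excess alone does not mark an error. But that excess is 0.1%, against 2.9% here. No rounding-up convention is stated, and the other rows cannot reveal one for the hours because their minutes convert exactly. Even if the figures arose this way, the printed minutes and maximum rate still do not match.
- **The digit may be misread.** The text was extracted from PDF by a program, and a column heading in this table is visibly broken. One wrong digit in the minutes would produce this pattern. No digit elsewhere in the table is visibly damaged, so this is possible but not shown.
- **The Pharmacy Manual may settle it, and the gap is small.** What the manual says about infusion times is unknown. The SAP's exposure and compliance summaries (Sections 7.6 and 7.7) use infusion counts, interruptions and dates, not infusion minutes or rates. Both points support a low severity; neither removes the discrepancy in the protocol.

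**Conclusion.** The concern holds as a minor arithmetic inconsistency, with medium confidence. One of the six rows of Table 4 contradicts itself by 4 minutes (140 against 144) and by 7.1 mL/hour (257.1 against 250, or 2.9%). The conclusion assumes that the digits were read correctly from the PDF and that the two columns are limits on the same infusion, as their headings say. The printed 600 mL, 2.4 hours and 250 mL/hour agree with one another and the 140 minutes does not agree with them, but that does not establish which entry is right, and no view is taken on it. No endpoint, sample-size figure or planned analysis is affected.

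**What to change.** First check the cell against the original PDF. If it is printed as shown, reconcile the minutes, hours and rate in this row with each other, with the controlling dosing source and with the Pharmacy Manual, and issue a protocol clarification for the row. If the table rounds hours or rates by a set convention, state it in a table note.

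The cost is low: one source check and, if the cell is confirmed, a clarification of one table row. Design, data collection and analysis do not change.

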# 6.2. Preparation/Handling/Storage/Accountability

Upon arrival of the study drug at the study site, study drug kits should be removed from the shipping container and stored in their original cartons under refrigerated conditions at 2°C to 8°C (35°F to 47°F) and protected from light. Ravulizumab should not be frozen.

Study drug must be stored in a secure, limited-access storage area with temperature monitored daily.

Infusions of study drug should be prepared using aseptic technique. Ravulizumab will be further diluted in a 1:1 ratio with compatible diluent. Ravulizumab will be filtered with a 0.2 micron filter during infusion. Study drug will be prepared and administered by a trained member of the site study team.

- 1. The investigator or designee must confirm appropriate temperature conditions have been maintained during transit for all study drug received and any discrepancies are reported and resolved before use of the study drug.
- 2. Only participants enrolled in the study may receive study drug and only authorized site staff may supply or administer study drug. All study drug must be stored in a secure, environmentally controlled, and monitored (manual or automated) area in accordance with the labeled storage conditions with access limited to the investigator and authorized site staff.
- 3. The investigator, institution, or the head of the medical institution (where applicable) is responsible for study drug accountability, reconciliation, and record maintenance (ie, receipt, reconciliation, and final disposition records).
- 4. For detailed instruction on study drug preparation, handling, storage, and accountability, refer to the Pharmacy Manual. Further guidance and information for the final disposition of unused study drug are provided in the Pharmacy Manual.

### 6.3. Measures to Minimize Bias: Randomization and Blinding

This is an open-label study. All study participants, site personnel, Alexion staff, designees, and all staff directly associated with the conduct of the trial will be unblinded to participant treatment.

### 6.4. Study Drug Compliance

Study drug will be administered in a controlled setting under the supervision of the Investigator or designee, thereby ensuring compliance with study drug administration.

The date and time of each dose administered in the clinic will be recorded in the source documents and recorded in the electronic case report form (eCRF). The dose of study drug and study participant identification will be confirmed at the time of dosing by a member of the study site staff other than the person administering the study drug.

### 6.5. Concomitant Therapy

Any medication including over-the-counter or prescription medicines, vitamins, and/or herbal supplements that the participant is receiving at the time of enrollment or receives during the study must be recorded along with:

- Reason for use
- Dates of administration including start and end dates
- Dosage information including dose and frequency

Prior medications (including vitamins and herbal preparations), including those discussed in the exclusion criteria (Section 5.2) and procedures (any therapeutic intervention, such as surgery/biopsy or physical therapy) the participant takes or undergoes within 28 days prior to the start of Screening until the first dose of study drug, will be recorded in the participant's case report forms. In addition, history of meningococcal vaccination must be collected for the 3 years prior to first dose of study drug.

Transfusions of packed red blood cells received within 1 year prior to first study drug administration will be recorded in the participant's eCRF.

All medications or therapies and procedures undertaken during the study will be recorded in the participant's source document/medical chart and eCRF. This record will include all prescription drugs, herbal products, vitamins, minerals, over-the-counter medications, and current medications for PNH. Concomitant medications will be recorded from the first infusion of study drug through 30 days after the participant's last dose of study drug. Any changes in concomitant medications also will be recorded in the participant's source document/medical chart and eCRF. Any concomitant medication deemed necessary for the participant's standard of care during the study, or for the treatment of any AE, along with the allowed medications described below may be given at the discretion of the investigator.

The following concomitant medications are allowed if the following conditions apply, and dose adjustments are not expected during the treatment period:

- Erythropoietin, if the participant has been receiving a stable dose for at least 8 weeks before Screening.
- Immunosuppressants, if the participant has been receiving a stable dose for at least 8 weeks before Screening.
- Corticosteroids, if the participant has been receiving a stable dose for at least 4 weeks before Screening.
- Vitamin K antagonists (eg, warfarin), if the participant has had a stable INR level (per investigator's discretion) for at least 4 weeks before Screening.
- Iron supplements or folic acid, if the participant has been receiving a stable dose for at least 4 weeks before Screening.

Adjustments in the frequency or dose level in any of the above medications can be made if the Alexion Medical Monitor or the Investigator deems it is in the best interest of the participant.

The Medical Monitor should be contacted if there are any questions regarding concomitant or prior therapy.

Participants must abstain from taking prescription or nonprescription drugs (including vitamins and dietary or herbal supplements) within 7 days (or 14 days if the drug is a potential enzyme inducer) or 5 half-lives (whichever is longer) before the start of study drug until completion of the follow-up visit, unless, in the opinion of the Investigator and Alexion, the medication will not interfere with the study.

Other concomitant medication may be considered on a case-by-case basis by the Investigator in consultation with the Medical Monitor, if required.

### 6.5.1. Meningococcal Vaccination

As with any terminal complement antagonist, the use of ravulizumab increases the participant's susceptibility to meningococcal infection (*N. meningitidis*). To reduce the risk of meningococcal infection, all participants must have been vaccinated against meningococcal infections within 3 years prior to initiating study drug.

Vaccines against serotypes A, C, Y, W135, and B, where available, are recommended to prevent common pathogenic meningococcal serotypes. Participants must be vaccinated or revaccinated according to current national vaccination guidelines or local practice for vaccination use with complement inhibitors (eg, eculizumab). Participant's vaccination status will be confirmed.

Vaccination may not be sufficient to prevent meningococcal infection. Consideration should be given per official guidance and local practice on the appropriate use of antibacterial agents. All participants should be monitored for early signs of meningococcal infection, evaluated immediately if infection is suspected, and treated with appropriate antibiotics, if necessary.

To increase risk awareness and promote quick disclosure of any potential signs or symptoms of infection experienced by the participants during the course of the study, participants will be provided a safety card to carry with them at all times. Additional discussion and explanation of the potential risks, signs, and symptoms will occur at specific time points as part of the review of the participant safety card and throughout the study as described in the Schedule of Activities (SoA [Section 1.3]).

### 6.5.2. Rescue Medicine

Not applicable.

### 6.6. Dose Modification

### 6.6.1. Supplemental Dosing

If a BTH event occurs during the Screening Period, the participant will be ineligible for the study. If a participant experiences BTH during maintenance treatment with ravulizumab, an additional weight-based maintenance dose of ravulizumab may be administered or the next scheduled maintenance dose may be accelerated as per Table 5 at the Investigator's discretion after discussion with the Medical Monitor.

 Table 5:
 Dosing Guidance for Patients with Breakthrough Hemolysis

			Timing of Subsequ Maintenance Dose	ent Dose after Next
Time of BTH	Supplemental Dosing	Next Maintenance Dose	if free C5 is < 0.5μg/mL	if free C5 is ≥ 0.5 μg/mL
$\leq$ 2 weeks after previous dose	Decision to be made based on results of Free C5 at Investigator's discretion	As per SoAª	As per SoA a	6 weeks after the last maintenance dose b
>2 to < 6 weeks after previous dose	Supplemental dose	As per SoA a	As per SoA a	6 weeks after the last maintenance dose b
$\geq$ 6 weeks after previous dose	Not applicable	Accelerate next dose at Investigator's discretion	As per SoAª	6 weeks after the last maintenance dose b

aTiming of next dose will be per SoA (Section 1.3)

b See Section 6.6.2

Abbreviations: BTH = breakthrough hemolysis; C5 = complement component 5; SoA = Schedule of Activities

### 6.6.2. Permitted Change in Dosing Interval

If a participant experiences a free C5-related BTH during maintenance treatment with ravulizumab, shortening the dosing interval to every 6 weeks (q6w) is permitted at the discretion of the Investigator after discussion with Alexion's Medical Monitor. For these participants, the assessments performed at the first q6w visit would be those indicated in the SoA (Section 1.3). Subsequent q6w visit assessments would continue to be aligned to the example visit illustrated in Table 3, with the EOS/ET visit being on/after Day 351. Between the SoA-specified visits occurring at 6-week dosing frequency and the EOS/ET visit, any additional visits are to be classified as unscheduled visits and would follow the study procedures for unscheduled visits (Table 3).

# 6.7. Intervention after the End of the Study

At the end of the study, participants will be transitioned to standard of care.

All participants will be followed for safety for an additional 16 weeks after the last dose of study drug if they discontinue from the study early.

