#### 2.3.1. Risk Assessment

Risks of Clinical Significance	Summary of Data/ Rationale for Risk	Mitigation Strategy
Potential Risks		
Serious hemolysis after drug discontinuation	This potential disease-associated risk is based on a theoretical possibility, associated with abrupt ravulizumab discontinuation, resulting in a so- called rebound effect. Rebound effect is described for many biologicals but has not been observed in ravulizumab clinical trials.	The effects are most likely not completely preventable, but their severity can be minimized by avoiding abrupt drug discontinuation. Participants who discontinue the drug will be followed up for 16 weeks if participants remain in the study.
Serious infection	This potential risk is a based on the mode of action of ravulizumab and experience with the use of eculizumab. Since the relevance of serious infection with ravulizumab therapy has not been confirmed in clinical trials, this remains a potential risk.	Increased awareness of healthcare professionals and participant about the potential risk of serious Infection. Monitoring for signs and symptoms of serious infections will be conducted as part of routine safety assessments for this study.
Malignancies and hematologic abnormalities	The natural evolution of PNH disease makes PNH patients more prone to development of hematologic abnormalities or malignancies as approximately 30-70% of PNH patients eventually develop aplastic anemia or myelodysplastic syndrome. The potential role of ravulizumab in the risk of such abnormalities or malignancies (if any) is unknown	Monitoring as part of routine safety assessments for this study.
Immunogenicity	Treatment with any therapeutic protein has the potential to induce an immune response. Potential clinical consequences may include severe hypersensitivity type reactions, decrease in efficacy and induction of autoimmunity, including antibodies to the endogenous form of the protein (Casadevall, 2002; Li, 2001). Protein therapies administered IV have the potential risk of causing local (infusion-site reactions) and systemic reactions (infusion-associated reactions).	In the ALXN1210-PNH-103 and ALXN1210-PNH-201 studies, no participants have returned a positive ADA sample. ADA will be assessed. Monitoring for infusion reactions will be conducted as part of routine safety assessments for this study.

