### 7.2. Participant Discontinuation/Withdrawal from the Study

All efforts should be made to ensure participants are willing to comply with study participation prior to conducting the screening procedures. The study staff should notify their site monitor and Alexion of all study withdrawals as soon as possible. The reason for participant discontinuation must be recorded in the source documents and eCRF.

If a participant withdraws consent, the assessments specified for the Early Termination (ET) visit (as shown in the SoA, Section 1.3) will be performed and Alexion and site monitor notified as soon as possible. Participants who withdraw from the study will not be replaced.

Participants should be permanently discontinued from ravulizumab treatment if any of the following occur during the study:

- Serious infusion reaction (such as bronchospasm with wheezing or requiring ventilator support or symptomatic hypotension) or serum sickness-like reactions manifesting 1 to 14 days after drug administration;
- Severe uncontrolled infection;
- Pregnancy or planned pregnancy; or
- If the Alexion Medical Monitor or the Investigator deems it is in the best interest of the participant.

The Investigator should speak with the Medical Monitor prior to discontinuing a participant's study treatment. If a participant is discontinued from study drug, the participant should be encouraged to return for the remainder of his or her scheduled protocol visits until starting a different complement-targeted therapy.

If a participant is discontinued from the study with an ongoing AE or an unresolved laboratory result that, in the opinion of the Investigator, is significantly outside of the reference range and
clinically significant (Section 10.3), the Investigator will attempt to provide follow-up until a satisfactory clinical resolution of the laboratory result or adverse event is achieved.

If a female participant is permanently discontinued from ravulizumab treatment due to pregnancy, the Investigator will attempt to follow-up until the outcome of the pregnancy (Section 10.4).

- A participant may withdraw from the study at any time at his/her own request or may be withdrawn at any time at the discretion of the Investigator for safety, behavioral, compliance, or administrative reasons. This is expected to be uncommon.

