- If the participant withdraws consent for disclosure of future information, Alexion may retain and continue to use any data collected before such a withdrawal of consent.
- If a participant withdraws from the study, he/she may request destruction of any samples taken and not tested, and the Investigator must document this in the site study records.

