# 8.3.1. Time Period and Frequency for Collecting Adverse Event and Serious Adverse Event Information

All AEs will be collected from the signing of the Informed Consent Form until the follow-up call.

All SAEs will be recorded and reported to Alexion or designee within 24 hours of awareness, as indicated in Section 10.3. The Investigator will submit any updated SAE data to Alexion within 24 hours of it being available.

Investigators are not obligated to actively seek AEs or SAEs after conclusion of the study participation. However, if the Investigator learns of any SAE, including a death, at any time after a participant has exited the study, and he/she considers the event to be reasonably related to the study drug, the Investigator must promptly notify Alexion.

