## 8.3.3. Follow-up of AEs and SAEs

After the initial AE/SAE report, the Investigator is required to proactively follow each participant at subsequent visits/contacts. All SAEs and AEs of special interest (AESI) (as defined in Section 8.3.6), will be followed until resolution, stabilization, the event is otherwise explained, or the participant is lost to follow-up (as defined in Section 7.3). Further information on follow-up procedures is provided in Section 10.3.

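### For a q6w participant who leaves the study early, the Table 3 follow-up call can end adverse event collection before the 16 weeks after last dose promised in Protocol 6.7

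*Protocol*

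**What the plan says.** - **The promise.** Under Protocol 6.7, every participant is to be "followed for safety for an additional 16 weeks after the last dose of study drug if they discontinue from the study early". The clock starts at the last dose.
- **The q6w schedule.** Table 3 (Protocol 1.3) has one contact timed after the EOS/ET visit: a follow-up call 56 days later, window ±7 days. Its clock starts at the visit, not at the last dose.
- **The end of collection.** Protocol 8.3.1 says "All AEs will be collected from the signing of the Informed Consent Form until the follow-up call". It adds that investigators need not actively look for events once participation has ended.
- **When ET can happen.** Protocol 6.6.2 describes the q6w schedule "with the EOS/ET visit being on/after Day 351". But Protocol 7.2 says "A participant may withdraw from the study at any time at his/her own request", and it requires the ET assessments when consent is withdrawn.
- **Follow-up of known events.** For an adverse event or significant laboratory abnormality still open when a participant leaves, Protocol 7.2 says the investigator "will attempt to provide follow-up until a satisfactory clinical resolution of the laboratory result or adverse event is achieved". Protocol 8.3.3 says SAEs and events of special interest "will be followed until resolution, stabilization, the event is otherwise explained, or the participant is lost to follow-up".
- **The q8w schedule.** Table 2 puts the follow-up call at Day 407 and gives no separate timing after an early ET.

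**The concern.** Section 6.7 and the schedule use different starting points. They agree only if the ET visit comes at least 56 days after the last dose. A q6w participant is due the next dose at 42 days, so an ET visit held at or before that visit leaves the call too early.

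Section 8 of the protocol makes adherence to the Schedule of Activities a requirement. A site that follows Table 3 and 8.3.1 to the letter therefore stops collecting adverse events before the 16 weeks are up, without breaching either. A new event in the uncovered weeks has no planned contact to find it.

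The group matters clinically. Section 6.6.2 allows q6w dosing only after a free C5-related breakthrough hemolysis, so these participants have already lost disease control once on ravulizumab.

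**Working it through.** **Inputs**
- Promised follow-up: 16 × 7 = 112 days after the last dose (Protocol 6.7).
- Call: ET + 56 days, window ±7 (Table 3).
- q6w visit: 42 days after the previous dose, window ±7 (6.6.2 and Table 3).
- q8w completer: last dose Day 295, final visit Day 351, call Day 407 (Table 2).

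**The plan's own figure first.** For a q8w completer, 351 + 56 = 407 and 295 + 112 = 407. In that schedule a call 56 days after the final visit is exactly 16 weeks after the last dose, because the dosing interval is itself 56 days.

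**The q6w early leaver.** Let g be the days from last dose to ET. The call falls at g + 56, and the shortfall is max(0, 112 − (g + 56)), which is positive when g < 56. With the call made at +7, the shortfall is max(0, 112 − (g + 63)), which is positive when g ≤ 48.

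| g (days) | Call, nominal | Call, window | Shortfall, nominal | Shortfall, call at +7 |
|---|---|---|---|---|
| 14 | 70 | 63–77 | 42 | 35 |
| 28 | 84 | 77–91 | 28 | 21 |
| 42 | 98 | 91–105 | 14 | 7 |
| 48 | 104 | 97–111 | 8 | 1 |
| 49 | 105 | 98–112 | 7 | 0 |
| 55 | 111 | 104–118 | 1 | 0 |
| 56 | 112 | 105–119 | 0 | 0 |

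So the shortfall is certain at 48 days or fewer, and avoidable by a late call at 49 to 55 days. From 56 days there is none at the nominal call day, although a call at −7 could still be early for g up to 62 (62 + 49 = 111).

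**ET held at a q6w visit.** With both windows, the call falls between 35 + 49 = 84 and 49 + 63 = 112 days. It reaches 112 only when both windows are used to their late end.

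**Calendar example (illustrative).** Suppose q6w dosing starts on study Day 183 and the last dose is on Day 225. Sixteen weeks ends on 225 + 112 = Day 337.
- ET on Day 239: call on 239 + 56 = Day 295, which is 42 days short.
- ET on Day 267: call on 267 + 56 = Day 323, which is 14 days short.

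**Who is not affected**
- q8w completers: 112 days, as above.
- q8w early leavers under Table 2 as written: Day 407 is at least 112 days after any nominal q8w dose, since the last is Day 295.
- q6w completers: with doses on Days 183, 225, 267 and 309, EOS on Day 351 and the call on Day 407, the gap is 407 − 309 = 98 days. Section 6.7 makes its promise to early leavers only, so this does not breach it.

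**The case against.** The strongest reply is that the commitment is already there. Section 6.7 states the 16 weeks, Table 3 does not forbid a later contact, and a site could add one. This is true, and the fault is a schedule cell out of line with a stated duty, not a missing duty. But no such contact is scheduled, and 8.3.1 tells the site that collection has ended.

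The affected group is also narrow. A participant must have a free C5-related breakthrough hemolysis, be moved to q6w at the investigator's discretion, leave the study and not merely the drug, have ET soon after a dose, and still accept contact. Section 7.2 expects withdrawal to be uncommon. It also foresees that some will refuse further data use ("If the participant withdraws consent for disclosure of future information"), and no schedule can bind them. This stands, and it sets the severity.

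Safeguards remain. Sections 7.2 and 8.3.3 continue follow-up of known events, and 8.3.1 still requires reporting of related SAEs learned of later. The treatment-emergent definition (Protocol 9.4.2.1, SAP 11.1) has no end date, so a late report would still be counted. These provisions handle events that are known or reach the site by chance; none seeks new ones.

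Three stronger readings are tempting, and the documents do not support them:
- **Every q6w ET before 56 days breaks the promise.** Not so: the ±7 window can rescue an ET at 49 to 55 days.
- **The q8w schedule has the same gap.** It would only if Day 407 were read as ET + 56 days, and Table 2 does not say that.
- **The mitigation for hemolysis after stopping the drug fails.** Section 2.3.1 says "Participants who discontinue the drug will be followed up for 16 weeks if participants remain in the study", so it makes no promise about those who leave the study.

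**Conclusion.** The conflict holds, and it is minor. For a q6w participant who leaves the study early and still agrees to contact, following Table 3 and 8.3.1 as written nominally gives less than the follow-up in 6.7 whenever ET is under 56 days from the last dose. The representative figure is 14 days short, at the nominal q6w visit. The 42-day figure assumes ET 14 days after a dose; the documents give no distribution of early ET times, so it is only an illustration.

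The group may be empty among about 20 participants. No efficacy result is affected: the efficacy endpoints run through Day 351, and for the primary, transfusion and hemoglobin endpoints SAP 8.1, 8.2.3 and 8.2.4 use data only up to withdrawal, apart from their rule for withdrawal due to lack of efficacy. The conclusion rests on the nominal visit days and on Table 3's call being the only scheduled contact after ET.

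**What to change.** In Table 3, for early terminations only, time the follow-up call at the later of ET + 56 days and last dose + 112 days, with a window of 0 to +7 days, for participants who still agree to contact. State in 8.3.1 that adverse event collection for these participants runs to that call. For g from 14 to 56 the call is then at day 112 (112–119); for g = 70 it is at day 126 (126–133).

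Leave completers and the Table 2 Day 407 call as they are. At most, add a note to Table 2 that an early leaver's call must not come before last dose + 112 days. The Table 3 rule should not replace Day 407. With a last dose on Day 127 and ET on Day 141, it would give max(141 + 56, 127 + 112) = Day 239, which is 407 − 239 = 168 days earlier than now.

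SAP 3.1 places the call two months after the last dose, which does not match the 112 days in Table 2. Correcting that phrase is optional, since it drives no analysis.

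The cost is one table cell and one sentence, and both can wait for the next amendment. For a few participants at most, the call comes later: by 14 days if ET is 42 days after the last dose, and by 42 days if it is 14.
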